- The incidence of generalized convulsion, arrhythmia, acute kidney failure and acute hepatic failure within 1-14 days.
- The incidence of the following events within 1-28 days.
 - thrombotic events (microangiopathy including capillary leak syndrome), disseminated intravascular coagulation, deep vein thrombosis, pulmonary embolism, cerebral vein thrombosis, peripheral thrombosis, thrombosis with thrombocytopenia and ischemic strokes, acute coronary syndrome (acute myocardial infarction, unstable angina, and new onset angina)
 - bleeding events including haemorrhagic stroke (no subarachnoid)
 - composite endpoint: Venous thrombosis (including pulmonary embolism and deep vein thrombosis)
 - composite endpoint: Arterial thrombosis (including acute coronary syndrome and ischemic stroke)
 - composite endpoint: stroke (including haemorrhagic and non-haemorrhagic stroke)
 - heart failure, and stress cardiomyopathy.
- The incidence of immune/inflammatory events: encephalitis (including acute demyelinating encephalomyelopathy and meningoencephalitis), Guillain-Barré Syndrome, Bell's palsy, immune thrombocytopenia, thrombocytopenia, transverse myelitis, and cardiac inflammatory disorders (including myocarditis and pericarditis) within 1-42 days.
- The incidence of sensorineural hearing loss within 1-60 days.
- The incidence of asthma exacerbation within 1-14 days.

Non-acute events (events expected to be recorded >60 days after vaccination)

- The incidence of new onset autoimmune thyroiditis, multiple sclerosis, acute aseptic arthritis, and type 1 diabetes mellitus within 1-365 days.

Newly identified AESI may be incorporated to the list of AESI to be investigated by the current study if a safety signal occurs.

Study Design

The study will comprise a feasibility assessment for a period of 12 months and a safety evaluation study.

This study is a retrospective observational study using electronic healthcare databases of various types in Europe. Eligible individuals will be included in the study from the start of Ad26.COV2.S vaccination in each participating country, and the study will end at the last date of data availability in each database. The AESIs included in this study are considered potential or identified safety risks following the administration of Ad26.COV2.S. The selected AESIs represent a heterogeneous group, including multiple organ systems and acute and chronic conditions.

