 - thrombotic events (microangiopathy including capillary leak syndrome), disseminated intravascular coagulation, deep vein thrombosis, pulmonary embolism, cerebral vein thrombosis, peripheral thrombosis, thrombosis with thrombocytopenia and ischemic strokes, acute coronary syndrome (acute myocardial infarction, unstable angina, and new onset angina),
 - bleeding events including haemorrhagic stroke (no subarachnoid),
 - composite endpoint: Venous thrombosis (including pulmonary embolism and deep vein thrombosis)
 - composite endpoint: Arterial thrombosis (including acute coronary syndrome and ischemic stroke),
 - composite endpoint: stroke (including haemorrhagic and non-hemorrhagic stroke)
 - heart failure, and stress cardiomyopathy.
- The incidence of immune/inflammatory events: encephalitis (including acute demyelinating encephalomyelopathy and meningoencephalitis), Guillain-Barré Syndrome, Bell's palsy, immune thrombocytopenia, thrombocytopenia, transverse myelitis and cardiac inflammatory disorders (including myocarditis and pericarditis) within 1-42 days.
- The incidence of sensorineural hearing loss within 1-60 days.
- The incidence of asthma exacerbation within 1-14 days.

Non-acute events (events expected to be recorded >60 days after vaccination)

- The incidence of new-onset autoimmune thyroiditis, multiple sclerosis, acute aseptic arthritis, and type 1 diabetes mellitus within 1-365 days.

Newly identified AESI may be incorporated into the list of AESI to be investigated by the current study if a safety signal occurs.

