8.2.4.2. SCRI Design

For analyses of outcomes assessed with the SCRI design, the following criteria must be met. Note that the study population for each outcome-specific analysis will thus be different.

- Received a dose of Ad26.COV2.S vaccine during the study period.
- Have experienced the corresponding AESI during the control or risk window (as defined in [Table 1](#))
- Have at least one day of follow-up in both the control and the risk window.
- Have at least 12 months of data/registration in the data sources prior to start of pre-vaccination control window.

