8.3.3. Evaluation of Safety Outcomes

The sponsor has created a list of AESIs based on current knowledge of the Ad26.COV2.S vaccine. [Table 1](#) lists and explains the AESIs to be ascertained in the study with specific risk windows. Background incidence rates for most of the data sources and AESIs are available on the VAC4EU dashboard <https://vac4eu.org/covid-19-tool/>. Definitions and codes are available on Zenodo (<https://zenodo.org/communities/vac4eu/>).

Table 1: AESI-Specific Risk Windows and Washout Periods for Patient Inclusion in the Study

Body System	AESI	Disease-specific washout period before the index date	Disease-specific risk window following the index date
Nervous and central nervous system	Encephalitis, including ADEM and meningoencephalitis	365 days	1-42 days
	Guillain-Barré Syndrome	365 days	1-42 days
	Transverse myelitis	365 days	1-42 days
	Bell's palsy	365 days	1-42 days
	Multiple sclerosis, including optic neuritis	365 days	1-365 days
	Sensorineural Hearing loss	365 days	1-60 days
	Generalised convulsion	365 days (w/o epilepsy) 90 days (w/o non-epileptic seizures)	1-14 days
Immune system	Autoimmune thyroiditis	365 days	1-365 days
	Immune thrombocytopenia	365 days	1-42 days
	Type 1 diabetes mellitus	Any time prior*	1-365 days
	Acute aseptic arthritis	365 days	1-365 days
	Anaphylaxis	90 days	0-2 days
Cardiac system	Cardiac inflammatory disorders, including myocarditis and pericarditis	365 days	1-28 days
	Microangiopathy	365 days	1-28 days
	Heart failure	365 days	1-28 days
	Stress cardiomyopathy	365 days	1-28 days
	Coronary artery disease, including acute myocardial infarction	365 days	1-28 days
	Arrhythmia	365 days	1-14 days
Blood and lymphatic system disorders	Deep vein thrombosis	365 days	1-28 days
	Pulmonary embolism	365 days	1-28 days
	Disseminated intravascular coagulation	365 days	1-28 days
	Non-haemorrhagic stroke	365 days	1-28 days
	Haemorrhagic Stroke	365 days	1-28 days
	thrombocytopenia	365 days	1-28 days
	peripheral thrombosis	365 days	1-28 days
	Sinus thrombosis	365 days	1-28 days
	Thrombotic Thrombocytopenia syndrome	365 days	1-28 days
	Composite: venous thrombosis	365 days	1-28 days
	Composite: arterial thrombosis	365 days	1-28 days
Composite: strokes	365 days	1-28 days	
Renal system	Acute kidney failure	365 days	1-14 days
Hepatic system	Acute hepatic failure	365 days	1-14 days
Respiratory system	Exacerbation of asthma	365 days	1-14 days

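### Thrombocytopenia and myocarditis/pericarditis have a 1-42 day risk window in the endpoint lists but 1-28 days in Table 1, and nothing says which prevails

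*Protocol*

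**What the plan says.** **Endpoint lists.** Section 7 of the protocol groups several immune and inflammatory events, thrombocytopenia among them, under one window. The list ends: "transverse myelitis and cardiac inflammatory disorders (including myocarditis and pericarditis) within 1-42 days". The abstract (Section 4) has the same list and the same window: "immune thrombocytopenia, thrombocytopenia, transverse myelitis, and cardiac inflammatory disorders (including myocarditis and pericarditis) within 1-42 days". Both sections call the listed items primary endpoints of the safety evaluation.

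**Table 1 (Section 8.3.3).** The row for cardiac inflammatory disorders, with washout and then risk window, reads "Cardiac inflammatory disorders, including myocarditis and pericarditis 365 days 1-28 days". The row for thrombocytopenia reads "thrombocytopenia 365 days 1-28 days". Immune thrombocytopenia has a separate row at 1-42 days, in agreement with Sections 4 and 7.

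**Where the window is used.** SCRI inclusion (Section 8.2.4.2) requires that a person "Have experienced the corresponding AESI during the control or risk window", with the windows taken from Table 1. Section 8.2.3 cites Table 1 for the start of the SCRI study period and of cohort follow-up. Section 8.1.2.1 gives the control window the same maximum length as the risk window. Table 5 (Section 8.7) names the SCRI with a post-vaccination control window, over the disease-specific risk window, as the primary analysis of acute events.

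**What is deferred.** Section 8.1.3 states that risk windows have been defined for every event. It leaves to the SAP only the extended windows for sensitivity analyses and the length of the buffer between risk and control windows.

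**The concern.** A primary endpoint and the table that the methods use to analyse it disagree by 14 days for two events. In an SCRI the risk window is part of the estimand. It determines which events count as cases, how long the control window is and, with a post-vaccination control, the earliest day on which that window can open. Changing 28 to 42 days changes all three.

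Timing adds to the problem. Both events are on the prioritised list for the first feasibility assessment (Section 8.3.2), and time-to-onset analysis without preset windows is a feasibility objective (Section 7). While two lengths stand in the protocol, onset data could end up deciding the primary window, a use the protocol does not intend.

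**Working it through.** **1. Is the conflict real?**

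| Event | Section 4 | Section 7 | Table 1 |
|---|---|---|---|
| Cardiac inflammatory disorders | 1-42 | 1-42 | 1-28 |
| Thrombocytopenia | 1-42 | 1-42 | 1-28 |
| Immune thrombocytopenia | 1-42 | 1-42 | 1-42 |

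The third row shows that the two thrombocytopenia entries have not been confused. The 42-day figure appears in two places and the 28-day figure in two separate table rows, so a single typing slip does not explain it. The amendment log in Section 3 records no change to these windows.

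**2. Reproduce the protocol's SCRI power.** Inputs: equal risk and control time (Section 8.5.2), so the risk-window share is r = 0.5. Alpha is not stated, so two-sided 5% is assumed. The signed-root likelihood-ratio formula is:

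- p = RR·r/(RR·r + 1 − r)
- A = 2[p·ln RR − ln(RR·r + 1 − r)]
- B = (ln RR)²·p(1 − p)/A
- power = Φ{[√(nA) − 1.96]/√B}

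For RR 2, A = 0.1133 and B = 0.9426. With n = 100 the power is 92.6% (Table 3: 92.6%). With n = 69 it is 80.5% (Table 4: 80.5%). For RR 1.5 and n = 200 it is 81.2% (Table 3: 81.2%). The formula matches.

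**3. Excess confined to days 1-28, 42-day window used.** This pattern is an assumption, with a constant rate outside the excess.

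- Expected rate ratio = (28×2 + 14×1)/42 = 70/42 = 1.67, instead of 2.0.
- Expected cases, in units of baseline rate × days: 28-day version 28×2 + 28 = 84; 42-day version 28×2 + 14 + 42 = 112.
- A population that supplies 100 cases in the 28-day version therefore supplies 100 × 112/84 ≈ 133 in the 42-day version.
- For a rate ratio of 1.67, A = 0.0632 and B = 0.9682. With n = 133 the power is 83%.

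Power falls from 93% to about 83%. Holding the count at 100 would give 71%, but that ignores the additional cases in the longer windows.

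**4. Excess lasting to day 42, 28-day window used.** The post-vaccination control window then has 28 days starting after a buffer of g days. It contains 14 − g at-risk days when g < 14 and none otherwise. With RR 2:

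- g = 14 or more: no bias, rate ratio 2.0.
- g = 7: control days 36-63, of which 7 are at risk. Mean relative rate in control (7×2 + 21)/28 = 1.25; rate ratio 2/1.25 = 1.60.
- g = 0 (limit): (14×2 + 14)/28 = 1.5; rate ratio 2/1.5 = 1.33.

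**The case against.** The strongest reply is that an analyst who follows the methods reaches one window. The rules that name a source for the windows (SCRI inclusion, the start of the SCRI study period, the start of cohort follow-up) all name Table 1, and Table 5 uses the same term as Table 1's column heading. On that view the endpoint list is a grouped summary that swept two events under the wrong number of days, out of more than 30 table rows. Much of this stands. A reader might infer two equally operative primary analyses, and the documents do not support that: the conflict is between the endpoint list and the methods. But the 42-day windows are part of what Sections 4 and 7 call the primary endpoints, and nothing ranks Table 1 above them.

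A reader might also take a rate ratio of 1.33 as the expected harm from the shorter window. That needs no gap at all, whereas Section 8.1.3 says the windows are separated by a buffer whose length the SAP will set. It is a limit, not a forecast.

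Finally, a reader might infer that the plan allows the primary window to be picked from onset data. It does not. Sections 8.1.3 and 8.7.1.1 use onset results for sensitivity windows only, and Section 8.7 requires an amendment for major changes to primary endpoint definitions. What remains is that these safeguards presuppose a single stated window, which these two events lack.

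**Conclusion.** The point holds as an internal contradiction in a primary endpoint definition for two prioritised events. It is not a matter left to the SAP, because the protocol says these windows are already defined.

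The size depends on the true onset pattern, which the documents do not give. With RR 2 confined to days 1-28, using the 42-day window moves the expected rate ratio from 2.0 to 1.67 and costs about 10 percentage points of power from a base of 100 cases. In the reverse case the bias depends on the buffer: none at 14 days or more, 1.60 at 7 days. These figures assume two-sided 5%, a constant baseline rate and complete follow-up of both windows. They show that the choice matters, not which length is correct.

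**What to change.** Reconcile the passages by protocol amendment so that thrombocytopenia and cardiac inflammatory disorders each have one primary risk window, entered identically in Section 4, Section 7 and Table 1. This review does not say which length is right.

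Make the choice without reference to the time-to-onset results, and give its grounds. A requirement to choose before any onset data are seen may no longer be achievable: Section 5 gives 10/11/2022 as the actual date of the first feasibility report, before Amendment 1 of 09 December 2022, and both events were on that report's list. Not every objective need appear in every report, so onset results may or may not have been shown. The amendment should therefore state which onset data from the feasibility reports had been seen when the window was chosen.

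Optionally, report the other length as a sensitivity window; Section 8.7.6 already provides for extended windows where the interval is not well known.

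The cost is wording in three places and a short statement of what was known. No new data are needed.

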8. RESEARCH METHODS

8.1. Study Design

The study will comprise a feasibility assessment, during a period of 12 months, and a safety evaluation study.

8.1.1. Feasibility Assessment

A feasibility assessment focusing on the availability of Ad26.COV2.S vaccine data (vaccine uptake), characteristics of individuals vaccinated with different COVID-19 vaccines and the measurement of AESIs will be conducted for each participating data source. From the start of the feasibility assessment, participating data sources will extract data twice (one extraction for the first feasibility assessment and one for the second feasibility and the final report). Summary reports (feasibility assessment reports and the final report) will be produced at each extraction. The primary design for the feasibility assessment will be a cohort study including all individuals with at least one day of follow-up after the start of Ad26.COV2.S vaccination in each participating country.

8.1.2. Overview of Study Design for Safety Evaluation Study

Evaluation of safety concerns will be conducted using a retrospective observational study in electronic health care databases of various types in Europe. Eligible individuals will be included in the study from the start of Ad26.COV2.S vaccination in each participating country, and the study will end at the last date of data availability in each database.

For each AESI, the study design of the safety evaluation study will depend on whether the AESI is an acute or non-acute event and follow the decision framework described in the ACCESS template protocols for evaluation of safety events in electronic health care databases ([Dodd 2020](#)).

The primary study design for the evaluation of acute events (events expected to occur within 2, 14, 28, 42, or 60 days of vaccination) will be a self-controlled risk interval (SCRI) design with pre- and post-vaccination control window and for non-acute events (events expected to occur within 365 days) will be a cohort design with concurrent unexposed comparators. Additionally, the cohort analysis will also include two active comparator groups: one viral vector vaccine comparator group (i.e., Vaxzevria[®] [AZD1222] by Oxford/AstraZeneca) and one mRNA vaccine comparator group (i.e., Comirnaty[®] [tozinameran] by Pfizer/BioNTech and/or Spikevax[®] [elasomeran] by Moderna), where possible (pending on the feasibility analysis with a maximum follow-up time of one year).

In sensitivity analyses, an equivalent cohort design will also be used to assess acute events. When it is established that data sources do not capture vaccinations well during the feasibility assessment, we will conduct a sensitivity analysis excluding these data sources from the cohort analysis with non-exposed comparators for the non-acute events, to avoid misclassification of exposure.

Another sensitivity analysis will compare the Ad26.COV2.S vaccine with active comparators (1) a 1-dose strategy and (2) a 2-dose strategy.

Individuals start follow-up at the start of each risk window and end follow-up at the earliest occurrence of latest data availability of the databank, individual exit from the database, completion of the study period, or death. At least one year of enrolment prior to the index date (date of vaccination) will be required to determine whether individuals meet the study criteria and to define baseline characteristics. If more historical data is available, this will be included.

[figure not shown]
8.1.2.1. Self-controlled Risk Interval Design (Primary Study Design for Acute Events)

The SCRI design will compare the risk of the AESI in a post-vaccination risk window to a pre-vaccination control window (sensitivity analysis) and post-vaccination control window (main analysis) within the same individual.

The SCRI design will include only individuals in the primary analysis who received at least one first-ever dose of the Ad26.COV2.S vaccine during the study period. Vaccinated individuals enter the study at the date of the start of the pre-vaccination control window. The SCRI design will compare the risk of each outcome during the post-vaccination risk window following the COVID-19 dose with a self-matched control interval that may be prior to vaccination, or after the vaccination risk window, to assess the baseline risk of the outcome. The control window will have the same maximum length as the risk window to minimise time-varying confounding that cannot be measured. In case the follow-up time does not capture the maximum post-vaccination risk or control window due to right censoring, all available follow-up time will be utilized. Follow-up will be censored upon vaccination with another COVID-19 vaccine or end of follow-up. A washout period between the control and risk window will be applied to minimise capturing of prevalent events during the risk window. A post-vaccination control window may induce a bias towards the null when an AESI that was identified during the vaccination risk window, is captured again during the control window due to a re-admission instead of reoccurrence of the AESI. This situation is more likely to be encountered for acute potentially recurring events such as cardiac events (including acute coronary syndrome, myocarditis, pericarditis, arrhythmia, and stress cardiomyopathy). Moreover, due to lag-times in updating the relevant databanks, there is a higher risk that the post-vaccination control window may not capture all events and underestimate the rate of events. Use of a pre-vaccination control window will deal with these issues. In a sensitivity analyses, we will use a pre-vaccination control window and a post-vaccination control window will be used for the main analysis. In a sensitivity analysis, vaccination to other non-COVID-19 vaccines will also be an exclusion and censoring event.

We will also compare the Ad26.COV2.S vaccine with active comparators with 1) only 1-dose strategy and 2) a 2-dose strategy.

[Figure 1](#) shows the SCRI study design diagrammatically using an example with a risk window and control window of 42 days.

Figure 1: Self-Controlled Risk Interval Design

T is time and T=0 is the index date.

8.1.2.2. Cohort Design (Primary Study Design for Non-acute Events and Sensitivity Analysis Design for Acute Events)

For the primary analysis of non-acute events, a retrospective cohort design will be used to estimate the rate of vaccination with Ad26.COV2.S vaccine, describe the characteristics of these vaccinated individuals and subsequently to estimate the incidence of new-onset autoimmune thyroiditis, multiple sclerosis, acute aseptic arthritis, and type 1 diabetes mellitus after receipt of the vaccine dose and to compare this incidence with that occurring in an unvaccinated matched comparator group, and in two groups of individuals exposed to other types of COVID-19 vaccines (i.e., one viral vector vaccine comparator group vaccinated [i.e., Vaxzevria[®] {AZD1222}] by Oxford/AstraZeneca) and one mRNA vaccine comparator group (i.e., Comirnaty[®] [tozinameran] by Pfizer/BioNTech and Spikevax[®] [elasomeran] by Moderna).

As a sensitivity analysis for acute events, a cohort analysis (following the same approach used in the main analysis for non-acute events) will be conducted.

- **Exposed cohort:** individuals will have received at least 1 dose of Ad26.COV2.S vaccine.
- **Concurrent unexposed cohort:** individuals that have not been vaccinated with Ad26.COV2.S vaccine or any other COVID-19 vaccine at any time prior to the index date (time zero) matched to the vaccinated individual for important characteristics as described in Section 8.7.2.1.
- **Cohort exposed to other COVID-19 vaccines:** individuals will have received at least 1 dose of a viral vector COVID-19 vaccine (i.e., Vaxzevria[®] [AZD1222] by Oxford/AstraZeneca) or an mRNA COVID-19 vaccine (Comirnaty[®] [tozinameran] by Pfizer/BioNTech and Spikevax[®] [elasomeran] by Moderna, respectively).

A sensitivity analysis will compare the Ad26.COV2.S vaccine with the active comparators with 1) a 1-dose strategy and 2) a 2-dose strategy.

In this retrospective cohort design, the start of follow-up will be defined as the time when study outcomes start to be counted. The index date in the exposed cohorts (i.e., recipients of the vaccines)

will be the day the first dose of the corresponding COVID-19 vaccination was received. This date in the unexposed group will be a day when an individual did not receive a COVID-19 vaccine dose and randomly chosen by calendar matching to the start date of the corresponding Ad26.COV2.S exposed individual (i.e., a random day during the same week that the matching individual in the exposed cohort receives the Ad26.COV2.S vaccine).

Individuals in the Ad26.COV2.S exposed cohort will be individually matched to one individual in the concurrent unexposed cohort and to one individual in each active comparator cohorts on key clinical variables (exact age, sex, previous COVID-19 infection and presence of one or more risk factors for severe COVID-19 [e.g., cancer, sickle cell disease, obesity, chronic kidney disease, chronic respiratory disease, human immunodeficiency virus infection], and month of vaccination (using calliper if needed)) at the index date.

[figure not shown]
Three sets of matched cohorts of individuals who meet all inclusion and exclusion criteria will be considered as follows:

- Recipients of a first Ad26.COV2.S dose matched to recipients of the first dose of a viral vector COVID-19 vaccine (AstraZeneca vaccine)
- Recipients of a first Ad26.COV2.S dose matched to recipients of the first dose of an mRNA COVID-19 vaccine (Pfizer-BioNTech or Moderna)
- Recipients of a first Ad26.COV2.S dose matched to unvaccinated individuals at the index date (individuals in this cohort may later become eligible to enter the exposed cohorts if vaccinated with a COVID-19 vaccine).

For the matched exposed cohorts, the index date (time zero) will be the date of the corresponding COVID-19 vaccine. For the unvaccinated individuals, the index date will be assigned as the index date of the matched exposed individual (see [Figure 2](#)). Additional details regarding matching will be included in the SAP.

Follow-up for unexposed persons is censored when the individual receives a COVID-19 vaccine. In a sensitivity analysis, vaccination with other non-COVID-19 vaccines will also be an exclusion and censoring event.

Figure 2: Schematic Overview of the Cohort Study Design

AESI = adverse event of special interest; COVID-19 = coronavirus disease 2019; FU = follow-up; SARS-CoV-2 = severe acute respiratory syndrome coronavirus-2.

Note: In the figure 1 year enrolment refers to the inclusion criterion to have at least 12 months of data available before the index date.

